- 2) Assess proposed mechanisms by which intervention strategy influenced adherence trajectory, including (1) participant self-efficacy, (2) medication responsibility, and (3) habit formation.
- 3) Explore caregiver and child perceptions of acceptability of intervention components and how they influenced adherence trajectory.

Study Design:

Basic design: Randomized controlled trial

Setting/Participants:

To accomplish the above objectives, we propose to enroll 125 children and their parents in a six-month intervention with a six-month follow-up period. Children will be ages 5-12, and must have two or more visits to any combination of the outpatient, ED or hospital setting in the past year for asthma exacerbations at Children's Hospital of Philadelphia.

Study Interventions and Measures:

[figure not shown]
The study intervention will include daily automated medication reminders (either via text message or push reminder), an app to track daily medication use, and nominal incentives to promote daily controller use. Inhaled controller medication adherence and rescue medication use will be measured using electronic monitors affixed to the inhalers. Factors associated with differential adherence will be assessed using surveys administered during enrollment, the experiment interval (months 2 and 4), the observation interval (month 7), and study completion (months 12-13). Efficacy outcomes will include change in parent-reported asthma control and mean adherence to ICS between study arms during the experiment interval, as well as the observation interval.

TABLE 1: SCHEDULE OF STUDY PROCEDURES

Study Phase	Screening and initial survey	Run-in period	Study survey	Experiment period			Study survey	Observation period	Study survey	Study completion survey
Visit Number	1 (clinic/hospital/phone)		2 (clinic/phone)				3 (clinic/phone)		4 (clinic/home phone)	5 (clinic/phone)
Arms	1,2,3	1,2,3	1,2,3	1	2	3	1,2,3	1,2,3	1,2,3	1,2,3
Study Month	0	0	2	1-3			4	4-6	7	12-13
Informed Consent/Assent	X									
Review Inclusion/Exclusion Criteria	X									
Demographics/Medical History	X									
Prior/Concomitant Medications	X									
Dispense Electronic Monitors	X									
Questionnaires	X		X				X		X	X
Child asthma control tool	X		X				X		X	X
Electronic monitoring		X		X	X	X		X	X	X
Daily medication reminders				X	X					
Adherence incentives				X						

FIGURE 1: STUDY DIAGRAM

A flow diagram of the study is included below.

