1.2 Name and Description of Investigational Product or Intervention

The intervention will be a three-arm randomized control trial that assesses the effects of different strategies for withdrawing financial incentives for ICS use targeting a cohort of children with multiple asthma hospitalizations in the preceding year. The intervention leverages mobile health technology to provide a daily cue (reminder message) and reward (feedback message with performance-based incentives) designed to reinforce routine ICS use.

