3.4 Study Population

3.4.1 Inclusion Criteria

- 1) Males or females age 5 to 12 years and their parent or legal guardian.
- 2) Caregiver has an app enabled cellular phone (i.e., smartphone)
- 3) Prescribed inhaled corticosteroid or corticosteroid/long acting beta agonist combination for daily use
- 4) At least 2 asthma exacerbations in the preceding year (Any combination of hospitalizations, ED visits, or outpatient visits where oral steroid courses were administered for asthma)
- 5) Parental/guardian permission (informed consent) and if appropriate, child assent.

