4.17 Sample Size and Power

Our analysis of pilot data demonstrates a 48% difference in ICS adherence when comparing a time interval with financial incentives (the same schema proposed in this study) to a time period without incentives. To ensure a power of 80% at a significance level of 0.05 to detect a more conservative 30% difference in average adherence between arms 1 and 3 in the *Experiment* phase (corresponding to 65% and 35%, respectively), 40 patients are required in each of these two arms. To ensure scientific rigor given the vulnerable nature of the population, we estimate ~20% loss to follow-up. Therefore, we will aim to enroll 50 participants in study arms 1 and 3 and 25 participants in arm 2, or 125 participants total, to achieve sufficient power to detect a difference between arms 1 and 3. The study is not to be powered to detect differences in arms 1 to 2 or 2 to 3 (hence the 2:1:2 randomization schema) or for health outcomes or cost offset; rather, it is intended to obtain preliminary estimates of marginal effects of the intervention components and effect sizes on utilization outcomes by comparing arm 1 to 2 and 2 to 3 to power a future multicenter study. Baseline data reveals that ~50% of children with at least 2 prior hospitalizations have a repeat ED visit or inpatient stay 6 months after the 2nd hospital discharge.

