7.6.1 Partial Waiver/alteration of HIPAA Authorization

We request a partial waiver of HIPAA authorization under 45 CFR 164.512(i.)(2)(ii).

Study staff propose to assess patient eligibility by screening the daily census of patients admitted to a General Pediatrics service at CHOP for patients 5-12 who have an admission diagnosis of asthma and for whom the asthma pathway order is activated using the Epic medical record.

(A) The use or disclosure of protected health information involves no more than a minimal risk to the privacy of individuals, based on the following elements:

1.) Plan to protect the identifiers from improper use and disclosure:

Only authorized study staff will access the Epic medical record for screening purposes. Information from the screening will be stored in a REDCap database only used by study staff.

2.) Plan to destroy the identifiers at the earliest opportunity consistent with conduct of the research:

For those who do not consent to study inclusion, protected health information will be deleted upon the family's decline or if the family is not enrolled in the study for other reasons (unable to approach parent for consent due to lack of parental availability). For those who do consent to be enrolled in the study, HIPAA authorization for the collection of PHI will be obtained at the time of enrollment.

3.) Protected health information will not be reused or disclosed:

Protected health information will not be reused or disclosed to any other person or entity, except as required by law, for authorized oversight of the research project, or for other research for which the use or disclosure of protected health information would be permitted.

(B) The research could not practicably be conducted without a partial waiver of HIPAA authorization.

There are over 2500 admissions for asthma on yearly basis at CHOP with hospital lengths of stay generally less than 24-48 hours, and each of these cases could be potentially eligible for recruitment. Given the limited time each patient is in the hospital and the number of potential patients, it would not be feasible to consent each of these 2500 for screening of their electronic medical records for eligibility.

(C) The research could not practicably be conducted without access to and use of the protected health information.

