7.6.2 Waiver of Consent

We request a Waiver of Consent under 45 CFR 46.116(d).

Study staff propose to assess patient eligibility by screening the daily census of patients admitted to a General Pediatrics service at CHOP for patients 5-12 who have at least 2 admissions for asthma OR 1 admission AND at least 1 ED visit in the last 365 days using the Epic medical record and Epic alerts and patient lists.

The research meets the criteria for a Waiver of Consent based on the following elements:

(A) The research involves no more than minimal risks to the subjects, based on the following 3 elements:

1.) Plan to protect the identifiers from improper use and disclosure:

Only authorized study staff will access the Epic medical record for screening purposes. Information from the screening will be stored in a REDCap database only used by study staff. 2.) Plan to destroy the identifiers at the earliest opportunity consistent with conduct of the research:

For those who do not consent to study inclusion, protected health information will be destroyed upon the family's decline or if the family is not enrolled in the study for other reasons (unable to approach parent for consent due to lack of parental availability). For those who do consent to be enrolled in the study, HIPAA authorization for the collection of PHI will be obtained at the time of enrollment via informed consent.

3.) Protected health information will not be reused or disclosed:

Protected health information will not be reused or disclosed to any other person or entity, except as required by law, for authorized oversight of the research project, or for other research for which the use or disclosure of protected health information would be permitted.

(B) The waiver will not adversely affect the rights and welfare of the subjects:

When potential participants are determined to be eligible for enrollment, a study team member will explain the study and ask if they would like to participate. Consent will be obtained in a HIPAA compliant manner, as described in the study procedures (see above Section 9.6). Participants will retain the right to choose whether they want to participate and provide consent. Patients who are deemed ineligible based on screening of the Epic medical record will not be approached for enrollment. The only information that will be retained for those screened ineligible will be the reason why they were deemed ineligible.

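### The waiver screening descriptions, section 1.2 and the abstract do not match the eligibility rule in 3.4.1, and the mixed-risk sample that rule allows calls for a named hospitalization covariate in the event and cost comparisons

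*Combined protocol and SAP*

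**What the plan says.** The formal criterion in 3.4.1 asks for at least two exacerbations in the preceding year and accepts "Any combination of hospitalizations, ED visits, or outpatient visits where oral steroid courses were administered for asthma". Section 7.5.1 gives the same rule. Section 3.1.1 screens the inpatient census against the inclusion and exclusion criteria, and adds a telephone route for children who qualify through outpatient visits.

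Four other passages describe the population differently:

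- Section 7.6.2 (waiver of consent) proposes screening admitted General Pediatrics patients with "at least 2 admissions for asthma OR 1 admission AND at least 1 ED visit in the last 365 days".
- Section 7.6.1 (HIPAA waiver) proposes screening admitted patients "who have an admission diagnosis of asthma and for whom the asthma pathway order is activated", with no count of earlier events.
- Section 1.2 describes the intervention as "targeting a cohort of children with multiple asthma hospitalizations in the preceding year".
- The abstract says children "must have two or more visits to any combination of the outpatient, ED or hospital setting in the past year for asthma exacerbations" at the study hospital, with no steroid condition.

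The plan gives one utilization rate, in 4.17: "Baseline data reveals that ~50% of children with at least 2 prior hospitalizations have a repeat ED visit or inpatient stay" within six months of the second discharge. The same section disclaims power for health outcomes and cost. Section 4.18 analyses time to the next asthma ED or inpatient visit from enrollment, by log-rank test, Cox models and an Andersen-Gill model for recurrent events. It compares costs as a difference in average totals between arms.

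**The concern.** A screen run as 7.6.2 describes would not look for some children whom 3.4.1 admits and whom 3.1.1 plans to telephone. A screen run to 3.4.1 would go beyond what either waiver describes. The choice of screen changes how many enrolled children have been hospitalized in the past year, and so to whom the results apply.

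The same breadth affects the secondary outcomes. Children with two admissions and children with two steroid-treated outpatient visits may differ in their risk of another ED or inpatient visit. The only event rate in the plan comes from the hospitalized end of that range. The plan does not name qualifying history as a covariate in the event models, and its cost comparison has no covariates.

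**Working it through.** **1. Passages side by side.** Three event types qualify under 3.4.1: hospitalization (H), ED visit (E) and steroid-treated outpatient visit (O). I read the steroid condition as attached to outpatient visits. Two qualifying events can be paired in six ways. For each pair, with no further events:

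| History | 3.4.1 / 7.5.1 | Abstract | 1.2 | 7.6.2 | Source group of the 50% rate |
|---|---|---|---|---|---|
| H + H | yes | yes | yes | yes | yes |
| H + E | yes | yes | no | yes | no |
| H + O | yes | yes | no | no | no |
| E + E | yes | yes | no | no | no |
| E + O | yes | yes | no | no | no |
| O + O | yes | yes | no | no | no |
| Two outpatient visits without steroids | no | yes | no | no | no |

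Section 7.6.2 covers 2 of the 6 pairs, and only for children on the current inpatient census. Section 1.2 and the source group of the event rate each cover 1 of 6. The abstract covers all six and adds a seventh history that 3.4.1 excludes, but limits visits to the study hospital. Section 7.6.1 does not fit the table: it takes any current asthma admission, whatever the history, and no child who is not an inpatient. These are counts of histories, not of children. The documents give no case mix.

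**2. Does the event rate enter the sample size?** Inputs from 4.17 are 65% against 35%, 80% power, significance level 0.05 and about 20% loss; 4.16.2 makes tests two-sided. Two proportions with unpooled variance:

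n = [0.65 × 0.35 + 0.35 × 0.65] × (1.960 + 0.842)² / 0.30² = 0.455 × 7.85 / 0.09 = 39.7, rounded up to 40 per arm.

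40 / (1 − 0.20) = 50 per arm, and 50 + 25 + 50 = 125. The plan's figures are reproduced, and the 50% rate appears nowhere in the calculation.

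**3. Does the 50% rate describe the trial population?** It differs in two respects. The source group (H + H) is a strict subset of 3.4.1. Its clock starts at the second discharge, whereas the clock in 4.18 starts at enrollment. No rate is given for the 3.4.1 population. As an illustration only, an assumed rate of 20%, 30%, 40% or 50% would give 10, 15, 20 or 25 children with an event in an arm of 50. N stays at 40, and 50 after loss, in every case.

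**4. How uneven could the arms be on prior hospitalization?** Section 7.1.1 uses blocks but names no stratification by history. If a share p of children had a prior-year hospitalization, the standard error of the between-arm difference in that share, treating allocation as simple, is √[p(1 − p)(1/n₁ + 1/n₂)]. The value of p is an assumption; I use 0.25 to 0.75.

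- Arms 1 and 3 (50 and 50): √(0.25 × 0.04) = 0.10 at p = 0.50; √(0.1875 × 0.04) = 0.087 at p = 0.25 or 0.75.
- Arms 1 and 2 (50 and 25): √(0.25 × 0.06) = 0.12 at p = 0.50; √(0.1875 × 0.06) = 0.11 at p = 0.25 or 0.75.

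Chance differences of about 10 percentage points would be unremarkable. An unadjusted difference in mean cost would carry them.

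**The case against.** The best defence is that the operative rule is clear. Sections 3.4.1 and 7.5.1 agree, 3.1.1 screens against those criteria and provides the outpatient telephone route, and 3.4.2 closes by barring anyone who does not meet all criteria. Section 1.2 is background, and the waiver texts describe chart screening, not enrollment. This stands. A reader might infer that the enrolled population is undefined; the documents do not support that. A child with two outpatient visits without steroids cannot be enrolled under 3.4.1, whatever the abstract says. What remains is that both waivers tie pre-consent screening to admitted patients. The mention in 7.6.2 of Epic alerts and patient lists does not supply the missing ED-only and outpatient routes.

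On the event rate, 4.17 does not call 50% the expected rate in the trial, and the outcome is declared unpowered. Recruitment favours hospital admissions, and the monitoring plan in Appendix 2 expects most enrolled children to have been hospitalized at some time. That stands too, and it limits how far the case mix is likely to move from the source group.

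On the covariate, 4.16.2 already compares past utilization between arms, the adjusted hazard models in 4.18 include covariates, and Aim 2 examines prior utilization. The intention is therefore there. But 4.18 points to covariates described earlier, and I found no such list in the text. A balance test does not adjust an estimate, and the cost comparison has no adjustment.

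**Conclusion.** The point holds as a contradiction between passages plus a gap in the secondary analyses. The screen in 7.6.2 covers two of the six pairs of events that 3.4.1 admits, 7.6.1 covers inpatients only, and 1.2 and the abstract each disagree with 3.4.1. Sample size and power for adherence are unaffected.

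A reader might go further and infer that the 50% figure overstates the precision of the utilization results, or the planning rate for the later multicenter study. The documents do not support either step. They state no precision for those outcomes. Section 4.17 looks to the trial's own estimates, not to the 50% figure, to power the later study. A lower rate in the broader population is plausible, but neither its size nor the case mix is given. The supported conclusion is only that the 50% rate may not apply to children enrolled under 3.4.1 and followed from enrollment.

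The case for the covariate rests on two assumptions: that prior hospitalization predicts later ED and inpatient use, and that the sample is mixed on it, as 3.4.1 permits.

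**What to change.** 1. Keep 3.4.1 as the governing criterion. Reconcile the abstract, 1.2, 7.6.1 and 7.6.2 with it, and describe the ED-only and outpatient routes in both waiver screening descriptions.
2. In 4.17, label the 50% rate as coming from children with at least two hospitalizations, timed from the second discharge, and say that it may differ in the 3.4.1 population followed from enrollment.
3. In 4.18, prespecify asthma hospitalization in the year before enrollment (yes/no) as a covariate in the adjusted Cox and Andersen-Gill models and in the between-arm cost comparison, for example by regressing cost on arm and this term. Define whether an admission during which the child is recruited counts.

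The cost is an amendment to the protocol and waiver wording and a few lines of analysis text. Section 4.11.1 already abstracts the number and dates of prior-year hospitalizations, so no new data are needed and N does not change.

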3.4.2 Exclusion Criteria

- 1) Subjects prescribed a controller medication to which the electronic device cannot affix: AirDuo (and generic AirDuo), QVAR Redihaler, Asmanex Twisthaler
- 2) Subjects in which the mobile app is not compatible with their smartphone model
- 3) Subjects with major developmental delays or disabilities
- 4) Subjects with comorbid chronic diagnoses that influence their asthma management such as cystic fibrosis, bronchopulmonary dysplasia, or cyanotic heart disease
- 5) Families with active Department of Human Services (DHS) involvement
- 6) Non-English speaking families
- 7) Parents/guardians or subjects whose medical team recommends against approaching for enrollment in a research study.

Subjects that do not meet all of the enrollment criteria will not be enrolled. Any violations of these criteria must be reported in accordance with IRB Policies and Procedures.

4 STUDY PROCEDURES

4.1 Technology Integration

To automate the computation of daily ICS adherence incentives and feedback for our study, we will first create a closed data loop connecting ICS puff actuation data from the electronic inhaler sensor and mobile health app with the Way to Health (WTH) platform. WTH is an NIH-sponsored, web-based platform that automates many of the research functions necessary for conducting randomized controlled trials of behavioral incentives. It has been used in numerous prior research studies.¹⁵⁻¹⁷ We will obtain the application programming interface (API) of the electronic inhaler actuation sensor (developed by Propeller Health, a sensor company with whom we have worked previously). We will work with WTH staff to program the computation of ICS adherence incentives and language of weekly adherence feedback messages to study participants. This integrated infrastructure will facilitate transmission of daily adherence data from the inhaler sensor platform to Way to Health via the sensor API.

Way to Health will use the adherence data to automatically tabulate financial incentives and send weekly adherence feedback messages to participants. We will collaborate with the engineering teams at WTH and Propeller to develop this integrated infrastructure. The WTH team has previously integrated 11 devices similar to this sensor for prior research studies.

4.2 Screening Visit (Visit 1)

- Note: For some participants Visit 1 may be completed in the hospital or at a follow-up visit in the month following hospitalization. This will be done 1) to accommodate participants' preferences and scheduling, and 2) to ensure that electronic monitors are provided when the child's asthma control inhaler is available for the device to be attached. For participants enrolled after physical distancing measures set in place for COVID-19, Visit 1 may be completed over the phone. This will be done 1) to ensure the safety of participants and study personnel, and 2) in accordance with hospital policy preventing study personnel from approaching patients in the hospital. In this circumstance, electronic monitoring devices will mailed to participants following telephonic enrollment.
- Informed Consent
- Epic Medical Record Review
- Study visit 1 survey question blocks (see section 4.11.2)
- Dispense and explain use of electronic monitoring devices
- Download and set up inhaler sensor app

4.3 Study Run-in Phase (Phase 1)

The study run-in phase will begin once families complete the screening visit. A study team member will instruct the family to use the inhaler as directed by their physicians and to care for the child's asthma as directed by the child's physicians.

Data collected during the study visits will be stored on the secure WTH web-based platform. Adherence monitoring data will be stored on the secure Propeller Health web-based platform and downloaded to WTH in real-time through the integrated API (see Section 7.2: Data Collection and Management for full descriptions of the WTH and sensor platforms, as well as the data management plan details).

4.4 Study Experiment Phase (Phase 2)

The child-caregiver dyads will be randomized into one of three arms for months 1-3: (1) receiving daily reminders, weekly feedback, and incentives, (2) receiving reminders and weekly feedback without incentives, or (3) receiving no reminders, feedback, or incentives. Participants will not know which group they are randomized to until they begin this phase of the study. Study participants will be contacted by telephone call or text message to inform them to which study arm they were randomized. At this time, study staff will help participants randomized to Arm 1 select an adherence reward goal of \$30 value.

4.5 Visit 2 (clinic or home preferred, telephone if not possible) – month 2

- Study visit 2 survey question blocks (see section 4.11.2)
- Equipment and medication refill check

4.6 Visit 3 (clinic or home preferred, telephone if not possible) – month 4

- Study visit 3 survey question blocks (see section 4.11.2)
- Semi-structured interview on intervention experiences and preferences
- Equipment and medication refill check

